6.5.2 Fluorouracil

6.5.2.1 Mechanism of action: Synthesis of 5-fluorouracil was first described by Heidelberger in 1957. 5-FU is considered to act primarily as an inhibitor of thymidylate synthetase.

6.5.2.2 Hepatotoxicity: Transient elevations in liver enzymes, especially SGOT (*AST*), and bilirubin, have been reported.

6.5.2.3 Formulation: 5-FU is commercially available in a liquid (concentration 50 mg/ml) in a 100 ml vial. It is stable if protected from light. If a precipitate is present, it is to be gently heated to no greater than 140°F in a water bath. In aqueous solution it is colorless to faint yellow, and is pH adjusted with sodium hydroxide to 8.6-9.0.

6.5.2.4 Preparation: An infusion pump should be used to control the infusion flow rate. The volume of diluent is dependent upon the particular type of pump used.

6.5.2.5 Storage: 5-FU should be stored at room temperature and protected from light.

6.5.2.6 Administration: continuous intravenous infusion.

6.5.2.7 Adverse Effects: Toxicities associated with the systemic administration of 5-FU include anorexia, nausea and vomiting, stomatitis, mucositis, phlebitis, diarrhea, myelosuppression, alopecia, rash, photosensitivity, maculopapular eruptions, hyperpigmentation, fingernail changes, neurologic symptoms,

-
cerebellar ataxia (rare), and very occasionally angina with accompanying EKG changes. “Hand and foot syndrome” has been observed in patients receiving continuous infusion 5-FU.

6.5.2.8 Supplier: Commercially available.

6.5.3 Chemotherapy Dose Schedule

Three cycles chemotherapy will be given with radiation therapy every 21 days.

Table 4. Dose schedule for cisplatin given with radiation

Agent	Dose	Route		Interval	Notes
Cisplatin	100 mg/m ²	I.V.		3 weeks (21 days)	Administered as per institutional standard

Three cycles of adjuvant cisplatin and 5-fluorouracil will be administered after radiation therapy. Adjuvant chemotherapy can be given between 3 - 8 weeks after the completion of radiation. If adjuvant chemotherapy is delayed due to treatment related toxicities beyond 8 weeks after the completion of radiation, then adjuvant chemotherapy will be deferred.

Table 5. Dose schedule for adjuvant cisplatin and 5-Fluorouracil given after radiation

Agent	Dose	Route	-	Interval	Notes
Cisplatin	80 mg/m ² /day	I.V.	-	4 weeks (28 days)	Administered as per institutional standard
5-Fluorouracil	1,000 mg/m ² /day	I.V.		4 weeks (28 days)	Mix according to institutional guidelines. Give as a 96 hour continuous infusion

Chemotherapy can be administered up to two days early or late if necessary for scheduling purposes.

6.5.4 Cisplatin Administration Guidelines:

- 6.5.4.1 Patients will be pre-hydrated with one liter of D5NS and 20 mEq KCl/L and MgSO₄ (2 gm/L). An oral equivalent dose of KCl is an acceptable option.
- 6.5.4.2 Cisplatin in 1000 ml of NS administered as per institutional standard. Ensure there is adequate urine output prior to cisplatin infusion. Mannitol of 12.5 gm may be given immediately before the administration of cisplatin or it can be given in cisplatin infusion. Furosemide 10 mg may be given as an intravenous bolus before cisplatin infusion. For adjuvant therapy after radiation, the cisplatin dose is 80 mg/m².
- 6.5.4.3 Patients should receive at least 3 liters of fluids over the ensuing 24 hours, either parenterally or orally. The anti-emetic regimens will be administered per institutional guidelines. In general, the antiemetics should include a 5-HT₃ antagonist (i.e. granisetron 750 mcg IV or 1 - 2 mg orally, or ondansetron 8 - 24 mg IV or orally). Additional antiemetics may include, but are not limited to, lorazepam, aprepitant, metoclopramide and/or prochlorperazine.

6.5.5 5-Fluorouracil Administration Guidelines:

Dose: 5-FU dose = 1000 mg/m²/24 hr as a 96 hour continuous infusion on days 1-4 of each 28 day cycle. A central intravenous line must be in place for those who receive the continuous 5-FU infusion as outpatients.

6.5.6 Cisplatin Dose Adjustments

6.5.6.1 Neutropenia

Treatment can be delayed for up to 2 weeks until ANC is $\geq 1500/\text{mm}^3$. However, if the counts have not recovered in 2 weeks, the patient should go off chemotherapy. Dose reductions for reduced ANC are not based on a single nadir count. The ANC must remain $< 500/\text{mm}^3$ for > 5 days before a dose reduction is made. If the results of the scheduled weekly complete blood count documents an ANC of $< 500/\text{mm}^3$, repeat counts are to be obtained every other day until the ANC recovers to a level of $> 500/\text{mm}^3$. If chemotherapy must be withheld due to neutropenia, complete blood count should be obtained weekly until the counts reach the lower limits for treatment as outlined.

Table 6. Cisplatin dose modifications in neutopenia

Nadir of last cycle		% Dose of cisplatin from starting dose
	ANC* on day 1 of each cycle < 1500	ANC* on day 1 of each cycle ≥ 1500
Febrile neutropenia (regardless of duration)	Hold	100%
< 500 for < 5 days	Hold	100%
< 500 for ≥ 5 days	Hold	80%

* ANC = absolute neutrophil count

ANC must be $\geq 1,500/\text{mm}^3$ on day 1 of each cycle. Reduce doses only for ANC is $< 500/\text{mm}^3$ for ≥ 5 days.

6.5.6.2 Thrombocytopenia

Chemotherapy must not be administered until platelets are $\geq 100,000$. If chemotherapy must be withheld due to thrombocytopenia, platelet counts should be obtained weekly until the counts reach the lower limits for treatment as outlined. Treatment is based upon the nadir count of the last cycle of chemotherapy as follows:

Table 7. Cisplatin dose modifications in thrombocytopenia

Nadir of last cycle		% Dose of cisplatin from starting dose
	Platelets on day 1 of each cycle < 100,000	Platelets on day 1 of each cycle ≥ 100,000
$\geq 50,000$	Hold	100%
< 50,000 (1 st occurrence)	Hold	80%
< 50,000 (2 nd occurrence)	Hold	60%

6.5.6.3 Peripheral neuropathy

-

A neurological examination must be performed at least before entry into the study and then once every cycle and when the patient goes off chemotherapy. In case of symptoms or signs experienced by the patient, more frequent examinations should be performed and dose modification will be as follows:

Grade 0 - 1: no change

Grade ≥ 2 : Decrease cisplatin dose by 50%. Carboplatin at an AUC of 6 may be substituted for cisplatin

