Appendix

- I Performance Status
- II Staging System
- III EORTC QLQ-C30 version 3
- IV EORTC QLQ-H&N
- V Tobacco and Alcohol Assessment/Pre-treatment
- VI Sialometric Form

Version 2.0

Date: 6.21.2011

- VII Physician Dysphagia Log
 - VIII Patient Swallowing Diary
 - IX Videofluoroscopic Swallowing (VFSS) Evaluation
 - X Common Terminology Criteria for Adverse Events, Version 3.0 (CTCAE)
 - XI Speech Assessment/Head and Neck Health Status Assessment Inventory (HNHSAI)
 - XII ChemoSensory Questionnaire (CSQ)
 - XIII Trismus Assessment
 - XIV Audiology Form
-

SCHEMA

**A Phase II Study of Proton Radiotherapy with Chemotherapy for
Nasopharyngeal Carcinoma**

[figure not shown]
Combined Proton-Photon Radiotherapy

Primary site	70 CGE
Nodal Disease > 2cm	70 CGE
Nodal Disease 1 - 2cm	66 CGE
Primary subclinical	60 CGE
High risk nodal region	60 CGE
Low risk nodal region	50 CGE

Chemotherapy

Cisplatin 100mg/msq d1 (cycle 1), 22 (cycle 2), 43 (cycle 3)
5-FU 1000mg/msq 96hr
Cisplatin 80mg/msq

I. Concurrent Radiotherapy and Chemotherapy (Chemoradiation)

RADIOTHERAPY* Days 1  54
CISPLATIN** X

*Administered Monday through Friday, start date may be on a Monday, Tuesday, Wednesday, or Thursday

* *Cisplatin infusion to be given every 21 days during RT. First dose to be administered within the first three days of the start of radiation.

II. Adjuvant Chemotherapy – to begin 3 - 8 weeks after completion of chemoradiation

Day	1	2	3	4	29	30	31	32	57	58	59	60
Cisplatin	x				x				x			
5-FU	x	x	x	x	x	x	x	x	x	x	x	x

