- 6.5.1.8 Ototoxicity: Ototoxicity has been observed in up to 31% of patients treated with a single dose of cisplatin 50 mg/m². It is manifested by tinnitus and/or hearing loss in the high frequency range. Deafness has been reported rarely.
- 6.5.1.9 Hematologic Toxicity: Myelosuppression occurs in 25 - 30% of patients treated with cisplatin. Nadirs in circulating platelets and leukocytes occur between Days 18 and 23 with most patients recovering by Day 39 or sooner. Thrombocytopenia, anemia, neutropenia, and fever are also possible adverse events. The occurrence of acute leukemia has been reported rarely in patients treated with anthracycline/alkylator combination chemotherapy.
- 6.5.1.10 Gastrointestinal Toxicity: Marked nausea and vomiting occur in almost all patients treated with cisplatin. Diarrhea and anorexia have also been reported.
- 6.5.1.11 Neurotoxicity: Neurotoxicity, usually characterized by peripheral neuropathies, has been reported. Neuropathy usually occurs after prolonged therapy (4 to 7 months); however, symptoms have been reported after a single dose. Muscle cramps, loss of taste, seizures, autonomic neuropathy, dorsal column myelopathy, and Lhermitte's sign have also been reported.
- 6.5.1.12 Ocular Toxicity: Optic neuritis, papilledema, and cerebral blindness have been reported infrequently in patients receiving standard recommended doses of cisplatin. Blurred vision and altered color perception have been reported after the use of regimens with higher doses of cisplatin or greater dose frequency than those recommended in the package insert.
- 6.5.1.13 Anaphylactic-like Reactions: Anaphylactic-like reactions have occasionally been reported in patients previously exposed to

-
cisplatin. Symptoms include facial edema, wheezing, tachycardia, and hypotension.

6.5.1.14 Hepatotoxicity: Transient elevations in liver enzymes, especially SGOT (*AST*), and bilirubin, have been reported.

6.5.1.15 Other Toxicities: Other infrequent toxicities that have been reported include cardiac abnormalities, hiccups, elevated serum amylase, rash, alopecia, malaise, and asthenia. Rare cases of local soft tissue toxicity have occurred.

6.5.1.16 Supplier: Commercially available.

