6.5.6.4 Otoxicity

Cisplatin is known to cause high frequency hearing loss. If grade 1 or 2 hearing loss occurs, the risk of additional hearing loss versus the potential benefit of continuing cisplatin chemotherapy should be made. If cisplatin is to be continued in the presence of grade 1 or 2 hearing loss, the dose of cisplatin should be decreased by 50%. Grade 3 and 4 hearing loss is an indication to discontinue the drug. In case of grade 3 or 4 toxicity, carboplatin (at dosage of AUC 6) may be used to replace cisplatin in the remaining chemotherapy cycles. The dose of carboplatin AUC 6 will be calculated based on the Calvert formula (table 9).

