6.5.7 Carboplatin Administration and Dose Adjustments

Carboplatin may be substituted for cisplatin if a patient develops 1) grade 3 or higher ototoxicity, 2) grade 2 or higher peripheral neuropathy, or 3) an unacceptable cisplatin-associated nausea and vomiting after receiving 1 or 2 doses of cisplatin. In the event of carboplatin-induced ≥ 3 neurotoxicity, carboplatin is discontinued.

Carboplatin is available commercially. It should be stored and reconstituted according to standard pharmacy operating procedures.

Carboplatin will be infused over 1 to 2 hours. Carboplatin dosage (mg) will be calculated for a target AUC 6 using the Calvert formula (table 9). Creatinine clearance (CrCl) will be calculated using the Cockcroft-Gault equation (table 10).

For females, use 85% of the calculated CrCl value. The actual body weight in kilograms will be utilized in the Cockcroft-Gault formula (table 10). However, if the calculated creatinine clearance exceeds an upper limit for creatinine clearance, as specified below, then this ceiling value for creatinine clearance, rather than the calculated creatinine clearance, will be used in the Calvert formula to calculate the dose of carboplatin. The maximum creatinine for both male and female patients is 125ml/min. Alternatively, at the treating physician's discretion, a measured 24-hour creatinine clearance can be obtained. In this case, the measured creatinine clearance can be used to calculate the carboplatin dose in the Calvert formula (table 9).

Table 9. Calvert formula for calculation of carboplatin dosage

$\text{Dose of carboplatin (mg)} = \text{AUC} \times [\text{CrCl (ml/min)} + 25]$

Table 10. Cockcroft-Gault equation for calculation of creatinine clearance (CrCl)

$$\text{CrCl (ml/min)} = \frac{(140 - \text{age}) (\text{wt kg})^*}{72 \times \text{serum creatinine (mg/dl)}}$$

* For female, the equation needs to be multiplied by 0.85.

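### The cisplatin neuropathy rule has one tier for grade 2 and above, so half-dose cisplatin remains permitted at grade 3-4, where hearing loss of that grade is an indication to stop

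*Combined protocol and SAP*

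**What the plan says.** Section 6.5.6.3 sets two tiers for cisplatin. Grade 0-1 neuropathy changes nothing. For grade 2 or higher the instruction is: "Decrease cisplatin dose by 50%. Carboplatin at an AUC of 6 may be substituted for cisplatin". Monitoring is specified in the same section: "A neurological examination must be performed at least before entry into the study and then once every cycle", with more frequent examinations if symptoms or signs appear.

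Three other places bear on the point:

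- Section 6.5.6.4, on hearing loss, separates the grades. Cisplatin is halved if it is continued at grade 1 or 2. Above that, "Grade 3 and 4 hearing loss is an indication to discontinue the drug", and carboplatin AUC 6 may replace it.
- Section 6.5.7 lists the conditions under which carboplatin may be substituted, among them "2) grade 2 or higher peripheral neuropathy". It also has a stop for the substitute itself: for carboplatin-induced toxicity rated 3 or more, the text reads "neurotoxicity, carboplatin is discontinued".
- Section 6.5.1.11 describes the timing of the cisplatin effect: "Neuropathy usually occurs after prolonged therapy (4 to 7 months); however, symptoms have been reported after a single dose".

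Exclusion 3.2.9 bars patients with symptomatic neuropathy of grade 2 or higher, but it applies only at entry.

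**The concern.** A single open-ended tier treats grade 4 neuropathy exactly like grade 2. A site that follows the written rule may give more cisplatin, at half dose, to a patient who already has severe neuropathy from it. The carboplatin switch is offered but optional, so it does not act as a stop.

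This is out of line with the rest of section 6.5.6. The rules for neutropenia, platelets and creatinine clearance each include a hold, and the hearing-loss rule includes discontinuation. Neuropathy has neither, and no reason is given. The rule has to serve more than one team, because section 6.0 lets patients receive chemotherapy at any participating institution.

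What is at stake is patient safety, in a small number of patients. No power, significance level or decision rule in section 12.0 depends on it.

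**Working it through.** The plan states no figure to reproduce. The check has two parts: the rules side by side, then the dose that a stop would prevent.

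**1. Cisplatin rule by grade**

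| Grade | Neuropathy (6.5.6.3, 6.5.7) | Hearing loss (6.5.6.4, 6.5.7) |
|---|---|---|
| 1 | 100% | 50% if cisplatin is continued |
| 2 | 50%, or optional carboplatin AUC 6 | 50% if cisplatin is continued |
| 3-4 | 50%, or optional carboplatin AUC 6 | Indication to discontinue; optional carboplatin AUC 6 |

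Nothing elsewhere in the documents stops cisplatin for neuropathy. Section 6.5.7 repeats the option to substitute without adding a duty to stop.

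**2. Cisplatin still permitted when severe neuropathy is found**

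Inputs:
- Radiotherapy runs from day 1 to day 54 (Schema).
- Adjuvant treatment is "to begin 3 - 8 weeks after completion of chemoradiation" (Schema; section 6.5.3 gives the same window).
- Adjuvant cisplatin is 80 mg/m² every 28 days for three cycles (section 6.5.3), so a half dose is 0.5 × 80 = 40 mg/m².
- Usual onset is 4 to 7 months (section 6.5.1.11), taken here from day 1 at 30.4 days per month: day 121.6 to day 212.8, a window of 91.2 days.

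Adjuvant schedule without delays:

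| | Earliest start (3 weeks) | Latest start (8 weeks) |
|---|---|---|
| Cycle 1 | 54 + 21 = day 75 | 54 + 56 = day 110 |
| Cycle 2 | 75 + 28 = day 103 | 110 + 28 = day 138 |
| Cycle 3 | 103 + 28 = day 131 | 138 + 28 = day 166 |

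Found at 4 months (day 122):
- Earliest start: only cycle 3 remains, 1 × 40 = 40 mg/m².
- Latest start: cycles 2 and 3 remain, 2 × 40 = 80 mg/m².
- The change comes when cycle 2 falls after day 121.6, that is, when adjuvant treatment starts after day 121.6 − 28 = 93.6, or (93.6 − 54) / 7 = 5.7 weeks after radiotherapy.
- Under a stop rule: 0 in each case.

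Share of the usual onset window that precedes the last dose:
- Earliest start: (131 − 121.6) / 91.2 = 9.4 / 91.2 = 10%.
- Latest start: (166 − 121.6) / 91.2 = 44.4 / 91.2 = 49%.

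Neuropathy found after the last dose (131 / 30.4 = 4.3 months to 166 / 30.4 = 5.5 months) is not affected by the rule.

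Early onset, which section 6.5.1.11 says has been reported after a single dose:
- Found before adjuvant cycle 1: 3 × 40 = 120 mg/m².
- Found before concurrent cycle 2, with two concurrent half doses of 0.5 × 100 = 50 mg/m² to come: 2 × 50 + 3 × 40 = 220 mg/m².

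**3. Sensitivity to the end of radiotherapy**

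Thirty-five weekday fractions from a Monday start, without interruption, end on day 6 × 7 + 5 = 47. Every adjuvant date then moves 7 days earlier, and cycle 3 falls on days 124 to 159. At day 122 the remaining dose is still 40 mg/m² (cycle 3 on day 124) to 80 mg/m² (cycles 2 and 3 on days 131 and 159). The share of the onset window becomes 2.4 / 91.2 = 3% to 37.4 / 91.2 = 41%.

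**The case against.** The strongest reply is that the hazard is already largely handled. Patients are examined every cycle, the dose is halved at grade 2, and a full switch to carboplatin is open from that grade. Someone who worsens gradually would reach grade 3 on half dose or on carboplatin. What remains is a physician who sees severe neuropathy, has a named substitute, and still chooses cisplatin. This stands as a limit on how many patients are affected. It does not close the gap: section 6.5.6.4 also offers carboplatin at grade 3-4 and still makes discontinuation of cisplatin the indicated course.

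A second reply is that the two rules differ in both directions. Carboplatin is offered from grade 2 for neuropathy but only from grade 3 for hearing loss, which could reflect deliberate toxicity-specific choices. The hearing-loss wording is also softer than the prohibitions used for platelets or for angina on 5-FU, and the carboplatin stop concerns toxicity caused by the substitute itself. These points soften the comparison, but none gives a reason to leave grade 3-4 neuropathy without a stop.

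Third, the timing figures are illustrative. Day 54 is the Schema's own figure but is late for 35 uninterrupted fractions, and an earlier end lowers the share of the onset window to about 3%-41%. The 4-to-7-month statement covers neuropathy of any grade, and severe grades may come later, when fewer doses remain. Nothing in the documents links these doses to a neurological outcome. All of this is fair. The milligram figures measure permitted exposure and do not estimate harm.

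**Conclusion.** The concern holds. As written, the protocol permits half-dose cisplatin at grade 3-4 neuropathy, and no other section stops it. At 4 months the rule leaves 40 to 80 mg/m² permitted, against 0 with a stop, whether radiotherapy ends on day 47 or day 54. Larger amounts arise only with early onset.

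The size rests on these assumptions: no treatment delays, no switch to carboplatin, no improvement before a later cycle, and onset counted from day 1. The number of patients affected is probably small, but it cannot be calculated because the documents give no on-treatment rate of grade 3-4 neuropathy. The reading of the rule is firm; the magnitude is indicative. This is a safety correction of limited reach that is worth making because it is cheap.

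**What to change.** In section 6.5.6.3, limit the 50% reduction to grade 2 and add a line that cisplatin is discontinued at grade 3-4, in parallel with section 6.5.6.4. Keep the carboplatin substitution that sections 6.5.6.3 and 6.5.7 already allow. Base the decision on the grade from the neurological examination already required each cycle.

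The cost is one line of text, with no new assessment and no new drug. A few patients may stop cisplatin earlier, which could slightly lower the number completing all six cycles, the count that section 12.0 compares with its minimum of 18 out of 25.

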6.5.6.4 Otoxicity

Cisplatin is known to cause high frequency hearing loss. If grade 1 or 2 hearing loss occurs, the risk of additional hearing loss versus the potential benefit of continuing cisplatin chemotherapy should be made. If cisplatin is to be continued in the presence of grade 1 or 2 hearing loss, the dose of cisplatin should be decreased by 50%. Grade 3 and 4 hearing loss is an indication to discontinue the drug. In case of grade 3 or 4 toxicity, carboplatin (at dosage of AUC 6) may be used to replace cisplatin in the remaining chemotherapy cycles. The dose of carboplatin AUC 6 will be calculated based on the Calvert formula (table 9).

6.5.6.5 Nephrotoxicity

If, despite adequate rehydration, serum creatinine increases to \geq grade 1 ($> 1.5 \times$ ULN), creatinine clearance should be recalculated before the next cycle and subsequent dose reductions will be considered as follows:

Table 8. Cisplatin dose modifications in kidney impairment

Calculated creatinine clearance (ml/min)		% Dose of cisplatin from starting dose
≥ 60		100%
< 60	0% (withhold treatment for a maximum of 2 weeks and repeat serum creatinine weekly after additional hydration), then	
	If *CCl was < 60 mL/min and is now:	The percent dose to give is:
	> 50 but < 60	80%

-	≥ 40 and ≤ 50	50%
	< 40	0%

* CCl = creatinine clearance

If creatinine clearance recovers, the dose of cisplatin for the following cycle should be re-escalated to the previous dose level.

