3.0 Subject Selection

3.1 Patient Eligibility

- 3.1.1 Biopsy proven stage \geq T2b and/or node positive (American Joint Committee on Cancer Sixth Edition, Stage IIB – IVB) non-metastatic, squamous cell carcinoma of the nasopharynx, types WHO I - III.
- 3.1.2 No head and neck surgery of the primary tumor or lymph nodes except for incisional or excisional biopsies.
- 3.1.3 Zubrod performance status 0 - 1 or Karnofsky 70 or above.
- 3.1.4 All patients must undergo pre-treatment evaluation of tumor extent and tumor measurement.
- 3.1.5 Nutritional and general physical condition must be considered compatible with the proposed chemoradiation treatment.
- 3.1.6 Signed study-specific informed consent prior to study entry.
- 3.1.7 Patients must have a WBC \geq 4,000/ μ l and a platelet count of \geq 100,000/ μ l; patients must have adequate renal function as documented by creatinine clearance \geq 60 ml/min (actual or calculated by the Cockcroft-Gault method).
- 3.1.8 Age 18 or above
- 3.1.9 No active alcohol addiction (as assessed by medical caregiver).

3.1.10 Women of childbearing potential must have a negative pregnancy test.

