6.5 Chemotherapy

6.5.1 Cisplatin

6.5.1.1 Mechanism of Action: The dominant mode of action of cisplatin appears to be inhibition of the incorporation of DNA precursors, although protein and RNA synthesis are also inhibited. Plasma levels of cisplatin decay in a biphasic mode with an initial half-life of 25 to 49 minutes, and a secondary phase ranging from 58 to 73 hours. This prolonged phase is due to protein binding which exceeds 90% of the radioactivity in the second phase. Urinary excretion is incomplete with only 27 to 45% of the radioactivity excreted in the first five days. The initial fractions of radioactivity are largely unchanged drugs. Although this drug seems to act as an alkylating agent, there are data to indicate that its mode and sites of action are different from those of nitrogen mustard and the standard alkylating agents.

6.5.1.2 Formulation: Cisplatin is available as a liquid (concentration 1 mg/ml) in a 100 ml vial.

6.5.1.3 Preparation: Aluminum reacts with cisplatin causing precipitation formation and loss of potency; therefore, needles or intravenous sets containing aluminum parts that may come in contact with the drug must not be used for the preparation or administration of cisplatin.

6.5.1.4 Storage: Cisplatin should be kept at room temperature to avoid precipitation. The solution may be further diluted in a chloride-containing vehicle such as D5NS, NS, or D51/2NS (precipitate occurs in D5W). Cisplatin has been shown to react with aluminum needles, producing a black precipitate within 30 minutes.

6.5.1.5 Administration: Cisplatin should be given immediately after preparation as a slow intravenous infusion.

6.5.1.6 Adverse Effects: Incidence rates of adverse events associated with cisplatin are provided in the product package insert. The following events are expected with the administration of cisplatin:

-

- 6.5.1.7 Nephrotoxicity: Dose-related and cumulative renal insufficiency is the major dose-limiting toxicity of cisplatin. Renal toxicity has been noted in 28 - 36% of patients treated with a single dose of 50 mg/m². It is first noted in the second week after a dose and is manifested as elevated BUN, creatinine, and serum uric acid, or as a decrease in creatinine clearance. Because renal toxicity becomes more prolonged and severe with repeated courses of cisplatin, renal function must return to normal before another dose can be given.

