9.0 Data Collection

Table 13. Evaluations before, during, and after chemoradiation

	Pre-study (timing before study entry)	Pre-treatment	During chemoradiation^b	During chemotherapy alone	Follow-up^c
History & physical	14 days		X	X	X
Disease	8 weeks				X

Version 2.0

Date: 6.21.2011

-

documentation	(*EUA)				
Dental evaluation		6 months			
Tobacco and alcohol assessment		14 days			
Nutritional evaluation		1 month			
Patient swallowing diary		14 days	X		1.5, 3, 12, 24 months ⁱ
CBC/platelets	14 days		X	X ^h	X
Chemistry (alkaline phosphatase ^a , AST, ALT, bilirubin, BUN, serum creatinine, creatinine clearance (if indicated), electrolytes (Na, K, Mg, Cl), calcium, protein, albumin, urinalysis (if indicated))	14 days		X (Weekly for BUN and creatinine. Every 3 weeks for the others)	X (Every 3 weeks)	
β-HCG for females at risk for pregnancy	14 days				
Thyroid function panel (TSH, T3, T4)	14 days				X ^l
Chest X-ray or CT	1 month				X ^d
CT/MRI of H&N	1 month				X ^d
PET/CT ^f		1 month			X
Toxicity evaluation			X	X ^c	X
Swallow study		21 days			3, 12, 24 months ⁱ
Salivary study		21 days			3, 6, 12, 24 months ⁱ
Speech assessment (HNHSAI)		14 days			1.5, 3, 6, 12, 24 months ⁱ
Subjective QOL		14 days			1.5, 3, 6, 12, 24 months ⁱ
Physician dysphagia log		14 days			1.5, 3, 6, 12, 24 months ⁱ

Audiogram	6 weeks				X ^g
Chemosensory questionnaire (CSQ)		14 days			1.5,3,6,12,24 months ⁱ
Trismus assessment		14 days			1.5,3,6,12,24 months ⁱ

* EUA = examination under anesthesia

X denotes the type of evaluation that needs to be performed during the study period.

- a. Liver CT or MRI must be done in presence of elevated alkaline phosphatase, AST, or bilirubin or other clinical indicator; bone scan must be done in presence of elevated alkaline phosphatase or other clinical indicator.
- b. Weekly during radiotherapy.
- c. Follow-up will be performed after radiation and then every 3 (+/- 3 weeks) months during the first two years; every 6 (+/- 3 months) months during years 3 - 5; then annually (+/- 6 months). After year 5, patients are encouraged to continue with the follow-up appointments and studies annually (+/- 6 months). All follow-up appointments and studies may be performed at non-participating institutions with results sent to the participating institutions for review.
- d. These tests will be performed at least every 6 months (+/- 3 months) during the first 3 years; the first CT/MRI of nasopharynx will be performed at approximately 2 months after radiation.

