- e. Prior to each cycle.
- f. PET/CT is optional but encouraged. It will be performed prior to treatment (must be ≤ 21 days prior to study entry), at approximately 2 months after radiation, and every 6 months during the first 3 years.
- g. Yearly (+/- 6 months) or clinically indicated. Once patients have reached the 24-month follow-up time point, patients are encouraged but not required to perform these studies at their annual (+/- 6 months) follow-up appointments.
- h. Every three weeks, or more frequently as clinically indicated. CBC/platelets must be drawn before treatment, either on day 1 of each cycle or no more than 72 hours in advance of each cycle.
- i. The 1.5 month studies will be performed at 1.5 (+/- 1) month after radiation, 3-month studies will be performed at 3 months (+/- 6 weeks), the 6-month studies will be performed at 6 (+/- 3) months, the 12-month studies will be performed at 6 (+/- 3 months), and the 24-month studies will be performed at 24 (+/- 6) months. Once patients have reached the 24-month follow-up time point, Patients are encouraged but not required to perform these studies at their annual (+/- 6 months) follow-up appointments.

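### Cisplatin renal rule: creatinine clearance need be recalculated only after creatinine exceeds 1.5 x ULN, by which point many eligible patients are already below the 60 ml/min hold level

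*Combined protocol and SAP*

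**What the plan says.** - **Entry (3.1.7):** "patients must have adequate renal function as documented by creatinine clearance" of at least 60 ml/min, measured or calculated by Cockcroft-Gault. There is no serum creatinine limit.
- **During treatment (6.5.6.5):** if creatinine goes above 1.5 x ULN despite rehydration, "creatinine clearance should be recalculated before the next cycle and subsequent dose reductions will be considered as follows". Table 8 gives 100% at 60 ml/min or more. Below 60 the instruction is to "withhold treatment for a maximum of 2 weeks and repeat serum creatinine weekly after additional hydration", then give 80% if clearance is above 50 but below 60, 50% if it is 40 to 50, and nothing below 40.
- **Formula (6.5.7, Table 10):** Cockcroft-Gault, multiplied by 0.85 for women.
- **Schedule (9.0, Table 13):** the chemistry row lists clearance only as "creatinine clearance (if indicated"). The frequency during chemoradiation is "Weekly for BUN and creatinine. Every 3 weeks for the others"; during adjuvant chemotherapy, chemistry is every 3 weeks.
- **Drug information (6.5.1.7):** "renal function must return to normal before another dose can be given". The term normal is given no number.
- **Blood counts, for comparison (Table 13, note h):** to be drawn "either on day 1 of each cycle or no more than 72 hours in advance of each cycle".

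**The concern.** The trigger is on the creatinine scale and the action threshold is on the clearance scale. The two coincide only for certain combinations of age, weight and sex. In a smaller, older or female patient, clearance crosses 60 well before creatinine reaches 1.5 x ULN, and in that interval no stated requirement brings Table 8 into play.

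Section 6.5.1.7 names renal insufficiency as cisplatin's major dose-limiting toxicity, dose-related and cumulative, and the regimen plans three cycles at 100 mg/m² and three at 80 mg/m². Under the literal rule, a patient with clearance of 40 to just under 60 can receive the next full dose where Table 8 would hold for up to two weeks and then give 80% or 50%. If 6.5.1.7 is not read as a limit, a patient below 40, whom Table 8 leaves at 0% after the hold, can also be dosed.

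**Working it through.** The plan states no figure on this point to reproduce, so the check uses its own formula.

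**Inputs.** Entry and hold level 60 ml/min (3.1.7, Table 8); lower bands 50 and 40 (Table 8); trigger 1.5 x ULN (6.5.6.5); CrCl = (140 − age) × weight / (72 × Cr), × 0.85 for women (Table 10). The documents give no ULN, so 1.0, 1.2 and 1.3 mg/dl are assumed.

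**Step 1: without a ULN.** At fixed age, weight and sex, clearance is inversely proportional to creatinine:

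CrCl at trigger = CrCl at entry × (Cr at entry) / (1.5 × ULN).

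This is below 60 when entry CrCl < 90 × ULN / (Cr at entry). So anyone entering at 60 to just under 90 ml/min with creatinine at or below ULN passes below 60 before the trigger. If entry creatinine is 0.75 × ULN, the limit is 90 / 0.75 = 120 ml/min, and everyone entering below 60 / 0.75 = 80 passes below 40.

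**Step 2: example patients.** For the 60-year-old, 70 kg man at ULN 1.2, the trigger is 1.5 × 1.2 = 1.8 mg/dl, and 80 × 70 / (72 × 1.8) = 43.2. For the 60-year-old, 60 kg woman, 0.85 × 80 × 60 / (72 × 1.8) = 31.5.

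| Patient | CrCl at trigger, ULN 1.0 / 1.2 / 1.3 | Cr at which CrCl = 60 | Cr at which CrCl = 40 |
|---|---|---|---|
| Man 60 y, 70 kg | 52 / 43 / 40 | 1.30 | 1.94 |
| Man 70 y, 70 kg | 45 / 38 / 35 | 1.13 | 1.70 |
| Woman 50 y, 60 kg | 42.5 / 35 / 33 | 1.06 | 1.59 |
| Woman 60 y, 60 kg | 38 / 31.5 / 29 | 0.94 | 1.42 |
| Man 30 y, 70 kg | 71 / 59 / 55 | 1.78 | 2.67 |
| Man 50 y, 90 kg | 75 / 62.5 / 58 | 1.88 | 2.81 |

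The last two rows show little or no gap. At ULN 1.2 the 60-year-old woman is below 40 from creatinine 1.42 up to the trigger at 1.8.

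**Step 3: how general this is.** The grid covers ages 20 to 75 and weights 50 to 100 kg in steps of 5, giving 12 × 11 = 132 cells per sex. It is not a patient distribution.

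| Cells of 132, ULN 1.0 / 1.2 / 1.3 | Men | Women |
|---|---|---|
| Below 60 at trigger | 60 / 90 / 101 (45%, 68%, 77%) | 87 / 112 / 120 (66%, 85%, 91%) |
| Below 40 at trigger | 11 / 25 / 38 | 24 / 51 / 64 |
| Below 60 with Cr = ULN | 11 / 25 / 38 (8%, 19%, 29%) | 24 / 51 / 64 (18%, 39%, 48%) |
| Below 40 with Cr = ULN | 0 / 1 / 3 | 1 / 7 / 12 |

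The second and third rows agree because 60/40 = 1.5. Keeping only cells that would be eligible at an assumed entry creatinine of 0.8 × ULN changes little: 45%, 66%, 74% of men and 64%, 82%, 88% of women are below 60 at the trigger.

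**Step 4: does 6.5.1.7 close the gap?** Suppose it means creatinine at or below ULN, with ULN 1.2.

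- The 60-year-old, 60 kg woman can enter at creatinine 0.90 (clearance 63). She is below 60 from 0.94, at 51.5 when creatinine is 1.10 (hold, then 80%) and at 47 when it is 1.20 (hold, then 50%).
- The 70-year-old, 70 kg man can enter at 1.0 (68), is below 60 from 1.13, and is at 57 at 1.20.
- The 60-year-old, 70 kg man has no gap on this reading (65 at 1.20).

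The gap narrows but stays open. The below-40 row is then rarely reached.

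**The case against.** The strongest reply is that 6.5.1.7 is wider than a creatinine limit. It counts a fall in clearance as one sign of renal toxicity and then demands a return to normal before redosing. Read with the 60 ml/min standard in 3.1.7, it would bar dosing below 60. That is a fair reading, but the text does not settle on it. It gives no number and schedules no calculation, and if normal meant 60 or more, the 80% and 50% rows of Table 8 could never be used. The sites giving chemotherapy would have to choose between two instructions.

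Second, nothing forbids an earlier calculation: Table 13 allows clearance when indicated, and creatinine is seen weekly during chemoradiation. Many clinicians would act on a rising value. But permission is not a requirement, and the only on-treatment trigger the protocol states for cisplatin is 1.5 x ULN. Prehydration and the urine-output check in 6.5.4 do not substitute for clearance. Adjuvant chemistry is already planned every 3 weeks, but cycles run every 28 days, so that creatinine is not tied to a dose.

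Third, the size depends on the assumed ULN. At 1.0 mg/dl rather than 1.2, the 60-year-old, 60 kg woman with creatinine at ULN is at 56.7 (80% band), not 47 (50% band), and her below-40 interval before the trigger shrinks from 1.42–1.8 to 1.42–1.5. This stands and is why a range is given. Nor do the grid shares say how often creatinine will rise that far.

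**Conclusion.** The concern holds and should be fixed. The written rule lets clearance fall below the protocol's own hold level before anyone must look at it. Across assumed ULNs of 1.0 to 1.3 mg/dl, 45% to 77% of male and 66% to 91% of female grid cells are below 60 at the trigger. Reading 6.5.1.7 as creatinine at or below ULN cuts this to 8% to 29% and 18% to 48%. Younger or heavier men may have no gap. These figures rest on the assumed ULN, on Table 10 with weight held fixed, and on an evenly weighted grid; they describe where clearance would be if creatinine rose, not how many patients will have renal impairment.

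The statistical consequence is limited. Section 11.0 counts courses received and section 12.0 asks for at least 18 of 25 patients to complete all six cycles, so a reduced dose still counts and only an omitted cycle changes the result. The effect on that count is likely small and was not quantified.

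**What to change.** 1. In 6.5.6.5, require clearance to be calculated from serum creatinine, age, weight and sex before every cisplatin cycle, with Table 8 applied whenever it is below 60 ml/min, whatever the creatinine grade.
2. In Table 13, replace the conditional entry for clearance with a calculation before each cisplatin cycle.
3. In 6.5.1.7, have the return-to-normal sentence refer to Table 8, so that only one rule applies.

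The cost is two sentences and one table entry in an amendment. Creatinine is already drawn weekly during chemoradiation; in the adjuvant phase it can be taken with the blood count already required within 72 hours of each cycle. The downside is that some cycles will be held, reduced or omitted. Only omissions, mainly in patients still below 40 after the hold, would lower the completion count.
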